8.4.3.3 Monotherapy Safety Assessment

The monotherapy safety assessment will include standard safety assessments (Section 8.4.3) occurring during the randomized withdrawal period. These analyses will be conducted during the randomized withdrawal period using the Randomized Withdrawal Subjects Data Set.

The reference time point to be used as 'withdrawal baseline' will be the closest time point on or before the third randomization visit.

The safety assessments will be compared within each treatment group from the original randomization as follows:

 For subjects initially randomized to the dapagliflozin (or saxagliptin) group, the subjects re-randomized to withdraw metformin will be compared to the subjects re-randomized to stay on metformin. Separate analyses will be performed for subjects respectively randomized to either the dapagliflozin or saxagliptin group.

- For subjects initially randomized to the placebo group, the subjects re-randomized to switch to
 dapagliflozin (or saxagliptin) monotherapy will be compared to the subjects re-randomized to
 stay on placebo with add-on metformin. Separate analyses will be performed respectively for
 subjects re-randomized to the dapagliflozin group and for those re-randomized to the
 saxagliptin group, using those re-randomized to placebo as comparator.
- Additional analysis will also be performed to compare all subjects taking dapagliflozin (or saxagliptin) monotherapy vs those taking placebo with background metformin during the randomized withdrawal period (adding placebo subjects randomized to withdraw metformin and switched to dapagliflozin [or saxagliptin]) monotherapy to dapagliflozin (or saxagliptin) subjects randomized to withdraw metformin).

For assessment of events, only those with an onset date occurring on or after the randomized withdrawal will be included in these analyses.

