- Eligible subjects who are receiving active treatment will be grouped into two separate strata for dapagliflozin and saxagliptin, and then randomised 1:1 within each strata to either discontinue background medication with metformin or to continue background medication with metformin. For subjects on active treatment who are randomised to withdraw background medication with metformin, those who are currently receiving high doses of saxagliptin (5 mg) or dapagliflozin (10 mg) will continue to receive the high doses, whereas subjects who are currently receiving low doses of saxagliptin (2.5 mg) or dapagliflozin (5 mg) will have their doses up-titrated to the high doses (saxagliptin 5 mg or dapagliflozin 10 mg). Subjects in the active treatment arms who are randomised to continue background medication with metformin will continue with their current dose of either saxagliptin or dapagliflozin.
- Eligible subjects who are receiving placebo will be randomised 1:1:1 to either withdraw background medication with metformin and switch to active treatment with either saxagliptin 5 mg or dapagliflozin 10 mg or to remain on background medication with metformin and continue with placebo.

[figure not shown]
The study design schematic for subjects not undergoing randomised withdrawal of background medication at Week 32 or Week 40 is presented in [Figure 2](#).

Figure 2 Study design schematic for subjects not undergoing randomised withdrawal of background medication at Week 32 or Week 40

The study design schematic for subjects undergoing randomised withdrawal of background medication at Week 32 or Week 40 is presented in [Figure 3](#).

[figure not shown]
Figure 3 Study design schematic for subjects undergoing randomised withdrawal of background medication at Week 32 or Week 40

*Subjects who fail to qualify at Week 26 due to HbA1c ≥ 7.5% at Week 26 may qualify at Week 32 if HbA1c < 7.5% at Week 32.

The subgroups following the third randomisation at Week 32 or Week 40 are presented in [Figure 4](#).

Figure 4 Subgroups following the third randomisation at Week 32 or Week 40

^a Subjects who fail to qualify for the third randomisation due to HbA1c ≥ 7.5% at Week 26 may qualify at Week 32 if HbA1c < 7.5% at Week 32.

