4.1.5 Treatment regimens

The following treatment regimens are considered for analysis:

- Low-dose/high-dose: Initial treatment of the low-dose (5 mg of dapagliflozin or 2.5 mg of saxagliptin) followed by up-titrating to the high-dose (10 mg of dapagliflozin or 5 mg of saxagliptin) for those who do not achieve the glycaemic target of HbA1c < 7% at Week 12 (not responding and re-randomised to high-dose) and continuing treatment with the low-dose for those achieving the glycaemic target of HbA1c < 7% at Week 12 (responding and not re-randomised; Groups I & III in [Figure 1](#)).
- Low-dose: Initial treatment of the low-dose (5 mg of dapagliflozin or 2.5 mg of saxagliptin) followed by continuing treatment on the low-dose drug for those who do not achieve the glycaemic target of HbA1c < 7% at Week 12 (not responding and re-randomised to low-dose) and those achieving glycaemic target of HbA1c < 7% at Week 12 (responding and not re-randomised; Groups I & II in [Figure 1](#)).
- Placebo, all subjects randomised to placebo.

Subjects who are receiving background medication with insulin only, or metformin + insulin (and who are therefore not eligible for the third randomisation) will continue with their randomised study medication assigned after the Week 12 assessment in the double-blind LT treatment period. After completion of assessments at Week 26, a subset of eligible subjects who are receiving background medication with metformin only will undergo a third randomisation (randomised withdrawal of background medication) at either Week 32 or Week 40. The following treatment comparisons are considered for this analysis:

- For subjects initially randomised to dapagliflozin (or saxagliptin): Initial treatment of the overall (combined low-dose and high-dose) dapagliflozin (or saxagliptin) with metformin compared to high-dose dapagliflozin (or saxagliptin) without metformin.
- For subjects initially randomised to placebo: Initial treatment of the placebo with metformin compared to high-dose dapagliflozin (or saxagliptin) without metformin.
- For all subjects, regardless of initial randomisation, based on third randomisation (for AE and marked abnormality [MA] laboratory analysis only).

For Week 104 analyses, subjects will be summarised based on both the first and last treatment received and also repeated for the subset of Week 104 completers (subjects who had the Week 104 visit).

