W_3 : For the weighted analyses, dapagliflozin (or saxagliptin) subjects who went through the third randomisation and withdrew metformin will be assigned a weight of zero, and those randomised to stay on metformin will be assigned a weight of 2. All other dapagliflozin (or saxagliptin) subjects will be assigned a weight of 1. Placebo subjects randomised to withdraw metformin and switch to active treatment will be assigned a weight of 0. Placebo subjects randomised to stay on metformin will be assigned a weight of 3. All other placebo subjects will be assigned a weight of 1.

- Safety analyses will be conducted during the randomised withdrawal period using the Randomised Withdrawal Subjects Data Set.

For subjects initially randomised to the dapagliflozin (or saxagliptin) group, the subjects re-randomised to withdraw metformin will be compared to the subjects re-randomised to stay on metformin. Separate analyses will be performed for subjects respectively randomised to either dapagliflozin or saxagliptin group.

For subjects initially randomised to the placebo group, the subjects who were re-randomised to switch to dapagliflozin (or saxagliptin) monotherapy will be compared to the subjects who were re-randomised to stay on placebo with background metformin. Separate analyses will be performed respectively for subjects re-randomised to dapagliflozin and for those re-randomised to saxagliptin, using the those re-randomised to placebo as comparator.

Additional analyses (for AEs, hypoglycaemic events, and MA labs only) will also be performed to compare all subjects taking dapagliflozin (or saxagliptin) monotherapy versus those taking placebo with background metformin during the randomised withdrawal period (adding placebo subjects randomised to withdraw metformin and switched to dapagliflozin [or saxagliptin]) monotherapy to dapagliflozin (or saxagliptin) subjects randomised to withdraw metformin).

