In addition, the overall AE summary will be repeated for subgroups based on race, ethnicity, sex, age group (using randomisation strata), region, baseline antidiabetic treatment, baseline HbA1c and baseline BMI, using the categories defined in the Appendix (Table 19). This will be provided based on the ST+LT period and will include all data regardless of rescue medication initiation and prior to rescue medication initiation. The overall AE summary will also be presented for the subgroup of subjects on a stable baseline dose of metformin IR or XR (with or without insulin).

The number and percentage of subjects with at least one AE will be summarised by SOC, PT and treatment group. AEs will be sorted by decreasing frequency within each SOC and PT according to the overall active treatment group, and, where applicable, by high dose active treatment or active treatment with background medication. As appropriate the number of events will also be displayed.

All adverse events will be summarised by SOC and PT (including incidence rate presented for PTs for the ST+LT period), regardless of rescue medication initiation unless otherwise specified, for:

- The ST period and the combined ST+LT period (including incidence rate).
- The ST period and the combined ST+LT period (including incidence rate), prior to rescue medication initiation.
- The combined ST+LT period, up to Week 32.

- The combined ST+LT period, excluding subjects randomised to withdrawal from metformin. A weighted analysis will be conducted on the Treated Subjects Data Set using the original randomised group and presenting weighted proportions.
- The combined ST+LT period. AEs will be summarised by treatment group received at the time of AE onset. For placebo subjects re-randomised to switch to dapagliflozin (or saxagliptin), AEs will be analysed in the placebo group to the beginning of the randomised withdrawal period and in the dapagliflozin (or saxagliptin) group if the event onset occurs during the randomised withdrawal period. AEs will be presented as incidence rate adjusted for exposure, as described in Section 3.4.1.
- The randomised withdrawal period. AEs with a date of onset occurring after the withdrawal baseline will be summarised using the Randomised Withdrawal Subjects Data Set separately for the three treatment comparisons described in Section 4.1.5.

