4.7.3 Laboratory evaluations

Safety laboratory evaluations performed by central laboratories will be included in summary tables and both central and local laboratory evaluations will be included in the listings. The laboratory data will be presented in Conventional (US) Units and additional presentations for changes from baseline will be repeated using SI units.

Summaries of laboratory data will include assessments up to the cut-off dates defined for each period and parameter in Table 8. Visit windows are provided in Section 4.1.7.1 in order to link each laboratory test to a scheduled visit. All continuous laboratory parameters specified in

Section 3.4.4 will be summarised at each scheduled time point by treatment group using descriptive statistics (including data regardless of rescue medication initiation) during:

- The combined ST+LT period. Observed and change from baseline values will be summarised by treatment group based on the treatment received during the ST period (dapagliflozin/saxagliptin/placebo) using the Treated Subjects Data Set.
- The combined ST+LT period, up to Week 32. Observed and change from baseline values will be summarised by treatment group based on the treatment received during the ST period (dapagliflozin/saxagliptin/placebo) using the Treated Subjects Data Set.
- The randomised withdrawal period. Observed and change from withdrawal baseline values will be summarised for the first two treatment comparisons described in Section 4.1.5 using the Randomised Withdrawal Subject Data Set.

Additionally, eGFR will also be described by age group (using the randomisation strata) for the ST+LT and randomised withdrawal periods using SI units.

Marked abnormality laboratory assessment will be summarised using central laboratories assessments during the ST, the combined ST+LT and randomised withdrawal periods for both conventional and SI units.

Haematology, chemistry and urinalysis laboratory data for the ST+LT period will be listed using both conventional and SI units where applicable. For the ST+LT + Week 104 period, the listing will include all data collected up to Week 104. Flags will be applied to values falling outside reference ranges (which will be explicitly noted on these listings where applicable). Treatment at the time of a laboratory assessment will be included in the listings and will correspond to the last dose received by a subject up to and including the date/time of the laboratory assessment.

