8.15 Overview of primary and sensitivity safety analyses

Table 24 Overview of primary and sensitivity safety analyses

Subgroup includes race, ethnicity, sex, age group using the randomisation strata, region, baseline antidiabetic treatment, baseline HbA1c, baseline BMI.

Parameter	Assessment	Short term period	Short term + Long term period	Withdrawal period: 1) For subjects initially randomised the dapagliflozin (or saxagliptin) group: High-dose dapagliflozin (or saxagliptin) vs High-dose dapagliflozin (or saxagliptin) + Metformin 2) For subjects initially randomised to the placebo group: High-dose dapagliflozin (or saxagliptin) vs Placebo + Metformin 3) Based on third randomisation (regardless of prior treatments)	Post-study visit Week 104
AEs	Overall AEs	Descriptive statistics + incidence rates Regardless of rescue Treated Subjects Data Set	Descriptive statistics + incidence rates Regardless of rescue Treated Subjects Data Set	Descriptive statistics + incidence rates Regardless of rescue Randomised Withdrawal Subjects Data Set For treatment regimens 1, 2 and 3	
		Sensitivity Descriptive statistics + incidence rates Prior to rescue Treated Subjects Data Set	Sensitivity Descriptive statistics + incidence rates Prior to rescue Treated Subjects Data Set	Sensitivity Descriptive statistics + incidence rates Prior to rescue Randomised Withdrawal Subjects Data Set For treatment regimens 1, 2 and 3	
			Up to Week 32 Descriptive statistics + incidence rates Regardless of rescue		

Parameter	Assessment	Short term period	Short term + Long term period	Withdrawal period: 1) For subjects initially randomised the dapagliflozin (or saxagliptin) group: High-dose dapagliflozin (or saxagliptin) vs High-dose dapagliflozin (or saxagliptin) + Metformin 2) For subjects initially randomised to the placebo group: High-dose dapagliflozin (or saxagliptin) vs Placebo + Metformin 3) Based on third randomisation (regardless of prior treatments)	Post-study visit Week 104
			Treated Subjects Data Set		
			Excluding subjects randomised to withdrawal Weighted analysis Treated Subjects Data Set		
			Subgroup Descriptive statistics + incidence rates Regardless of rescue Treated Subjects Data Set		
			Subgroup - Sensitivity Descriptive statistics + incidence rates Prior to rescue Treated Subjects Data Set		

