	Any serious adjudicated DKA events by adjudication category and PT	Descriptive statistics Regardless of rescue Treated Subjects Data Set	Descriptive statistics Regardless of rescue Treated Subjects Data Set	Descriptive statistics Regardless of rescue Randomised Withdrawal Subjects Data Set For treatment regimens 1 and 2	
Hypoglycaemia	Any hypoglycaemic events	Descriptive statistics Regardless of rescue Treated Subjects Data Set	Descriptive statistics Regardless of rescue Treated Subjects Data Set	Descriptive statistics Regardless of rescue Randomised Withdrawal Subjects Data Set For treatment regimens 1,2, and 3	
		Sensitivity Descriptive statistics Prior to rescue Treated Subjects Data Set	Sensitivity Descriptive statistics Prior to rescue Treated Subjects Data Set		
			Up to Week 32 Descriptive statistics Regardless of rescue Treated Subjects Data Set		

Parameter	Assessment	Short term period	Short term + Long term period	Withdrawal period: 1) For subjects initially randomised the dapagliflozin (or saxagliptin) group: High-dose dapagliflozin (or saxagliptin) vs High-dose dapagliflozin (or saxagliptin) + Metformin 2) For subjects initially randomised to the placebo group: High-dose dapagliflozin (or saxagliptin) vs Placebo + Metformin 3) Based on third randomisation (regardless of prior treatments)	Post-study visit Week 104
			Up to Week 32, Sensitivity Descriptive statistics Prior to rescue Treated Subjects Data Set		
Labs	Lab tests over time		Observed and change from baseline Regardless of rescue Treated Subjects Data Set	Observed and change from baseline Regardless of rescue Randomised Subjects Data Set For treatment regimens 1 and 2	
			Up to Week 32 Descriptive statistics Observed and change from baseline Regardless of rescue Treated Subjects Data Set		
		Shift table Based on LOCF values	Shift table Based on LOCF values		

Parameter	Assessment	Short term period	Short term + Long term period	Withdrawal period: 1) For subjects initially randomised the dapagliflozin (or saxagliptin) group: High-dose dapagliflozin (or saxagliptin) vs High-dose dapagliflozin (or saxagliptin) + Metformin 2) For subjects initially randomised to the placebo group: High-dose dapagliflozin (or saxagliptin) vs Placebo + Metformin 3) Based on third randomisation (regardless of prior treatments)	Post-study visit Week 104
		Treated Subjects Data Set	Treated Subjects Data Set		

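### SAP Table 24 names a withdrawal-period safety comparator, and in its laboratory rows analysis sets and a baseline, that contradict the SAP text and the protocol

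*SAP*

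**What the plan says.** At Week 32 or Week 40, eligible metformin-only subjects in each drug arm are re-randomised 1:1 to withdraw or continue metformin. Withdrawers on the low dose move to the high dose, so all withdrawers end up on the high dose. For the others, SAP 1.2 states: "Subjects in the active treatment arms who are randomised to continue background medication with metformin will continue with their current dose".

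The withdrawal-period safety comparison for drug-arm subjects is then described in these places:

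- **SAP 8.15, Table 24, withdrawal column, comparison 1:** "High-dose dapagliflozin (or saxagliptin) vs High-dose dapagliflozin (or saxagliptin) + Metformin".
- **SAP 4.1.5:** "Initial treatment of the overall (combined low-dose and high-dose) dapagliflozin (or saxagliptin) with metformin compared to high-dose dapagliflozin (or saxagliptin) without metformin".
- **SAP 4.7:** "the subjects re-randomised to withdraw metformin will be compared to the subjects re-randomised to stay on metformin", with no dose restriction.
- **Protocol 8.4.3.3:** "the subjects re-randomized to withdraw metformin will be compared to the subjects re-randomized to stay on metformin", again with no dose restriction.
- **SAP 8.13:** the output column for continuers pools 5 mg and 10 mg dapagliflozin plus metformin, and likewise 2.5 mg and 5 mg saxagliptin.
- **SAP Table 23:** the efficacy counterpart puts no dose on either side.

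The adverse event text in SAP 4.7.1.1 asks for summaries "separately for the three treatment comparisons described in Section 4.1.5".

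For laboratory values over time, and for eGFR, the withdrawal column of Table 24 reads "Observed and change from baseline Regardless of rescue Randomised Subjects Data Set". SAP 4.7.3 says "Observed and change from withdrawal baseline values will be summarised for the first two treatment comparisons", using the Randomised Withdrawal Subjects Data Set. SAP 4.7.3.1 again speaks of changes from baseline for the withdrawal period. The liver function and hepatic AE rows of Table 24 name the Randomised Subjects Data Set, and the marked-abnormality rows name the Treated Subjects Data Set. SAP 4.7 (in general) and 4.7.3.4 (for marked abnormalities) specify the Randomised Withdrawal Subjects Data Set.

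**The concern.** The third randomisation protects a comparison of all withdrawers with all continuers. A high-dose-only continuer group is not one of its arms. It would be a subset chosen by dose, with no matching selection among withdrawers, whose previous dose is hidden once all of them are on the high dose.

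The protocol has a stated safety objective on monotherapy in subjects randomised to withdraw metformin (Protocol 1.3.3), and these outputs serve it. In Table 24, DKA events and laboratory values over time are limited to comparisons 1 and 2. The third comparison, which the dose label does not touch, is therefore no fallback for them.

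The laboratory wording is a separate matter. SAP 4.1.1 defines baseline by the first dose on Day 1 and gives withdrawal baseline its own definition. Using the former would report change since the start of the study as change during the withdrawal period.

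**Working it through.** The plan states no figure to reproduce: it gives no count of third-randomised subjects by dose.

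**1. Who could be in a high-dose + metformin group.** Under SAP 1.2, subjects with Week 12 HbA1c below 7% stay on the low dose. Those at 7% or above are split 1:1 between low and high dose at Week 14. Before the third randomisation this is the only planned route to the high dose. Continuers on the high dose are therefore all Week 12 non-responders, while withdrawers include responders. This follows from the design without any assumption.

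**2. Share of continuers lost under a literal reading.** Let r be the Week 12 responder share. Let e1, eL and eH be the probabilities of reaching the third randomisation for responders, low-dose non-responders and high-dose non-responders. The low-dose share of continuers is

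L = [r·e1 + (1−r)/2·eL] / [r·e1 + (1−r)/2·(eL + eH)].

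All values of r and e below are assumptions.

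- *Equal eligibility:* L = (1 + r)/2, which is 50% at r = 0, 60% at r = 0.2 and 75% at r = 0.5.
- *e1 = 0.9, eL = eH = 0.25:* at r = 0.2, L = (0.18 + 0.10)/(0.18 + 0.20) = 0.28/0.38 = 74%. At r = 0.5, L = (0.45 + 0.0625)/(0.45 + 0.125) = 0.5125/0.575 = 89%.
- *Grid of 6 × 3 × 3 × 4 = 216 scenarios* (r from 0.1 to 0.6; e1 0.7, 0.8, 0.9; eL 0.1, 0.2, 0.3; eH 1, 1.5, 2 or 3 times eL, capped at e1): L runs from 36% to 97%. It exceeds 50% in 196 scenarios. In the other 20, r is 0.1 or 0.2 and high-dose non-responders are at least twice as likely to qualify as low-dose ones.

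At the low end (r = 0.1, e1 = 0.9, eL = 0.3, eH = 0.9): (0.09 + 0.135)/(0.09 + 0.54) = 0.225/0.63 = 36%. At the high end (r = 0.6, e1 = 0.9, eL = eH = 0.1): (0.54 + 0.02)/(0.54 + 0.04) = 0.56/0.58 = 97%.

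**3. Imbalance under a literal reading.** With e1 = 0.9 and eL = eH = 0.25, Week 12 responders are 0.18/0.38 = 47% of withdrawers at r = 0.2 and 0.45/0.575 = 78% at r = 0.5. They are 0% of a high-dose-only control group.

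**4. Laboratory baseline.** The withdrawal period lasts 52 − 32 = 20 weeks or 52 − 40 = 12 weeks. Change from Day 1 to Week 52 therefore includes 32 or 40 weeks that precede it.

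**5. Which laboratory rows are affected.** Only the rows for values over time and for eGFR are change-from-baseline rows. The liver, hepatic AE and marked-abnormality rows are descriptive counts, and SAP 4.7.3.2 rules out a comparison with baseline for elevated liver tests. Their conflict is in the analysis set alone.

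**The case against.** The strongest reply is that this is a label in an overview table and that the operative text already fixes the comparator. SAP 4.7 and Protocol 8.4.3.3 compare by third randomisation without regard to dose. Several sections of the SAP send their withdrawal-period summaries to 4.1.5. Section 8.13, which governs output columns, has no high-dose + metformin column. The adverse event, SAE, DKA and hypoglycaemia cells of Table 24 name the Randomised Withdrawal Subjects Data Set, which is everyone re-randomised, and nothing tells a programmer to exclude low-dose continuers. For the laboratory rows, comparisons 1 and 2 can contain only re-randomised subjects, so a broader data-set name adds nobody to them.

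Much of this stands. A reader might infer that the plan will drop most of the randomised controls and break the randomised comparison. The documents do not support that. It would happen only if the header overrode 4.1.5, 4.7, 8.13 and the data sets in its own cells, and the word most rests on eligibility rates that are nowhere documented. A reader might also infer that a Day 1 baseline biases the difference between arms. If all re-randomised subjects are kept, earlier change is balanced in expectation. It is the within-arm change figures that would be misdescribed.

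Two things remain. The DKA and elevated-liver sections (SAP 4.7.2.2 and 4.7.3.2) do not themselves cite 4.1.5, so Table 24 is the nearest statement of their comparator. And the baseline conflict lies in the body text as well, between 4.7.3 and 4.7.3.1, so deferring to the body does not settle it.

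**Conclusion.** The contradiction is real, and SAP Section 6 does not list it, although that section records two other departures from the protocol on the withdrawal period. A labelling error is the likelier explanation for the header. Its consequence is conditional: only if applied literally would it remove every low-dose continuer, and with them every Week 12 responder, from the control side alone. The size of that loss is undocumented. It is at least half if eligibility is unrelated to group, and 36% to 97% over the assumed scenarios.

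The laboratory inconsistency is more than a label. Two statements in the SAP (Table 24 and 4.7.3.1) point to one baseline and one (4.7.3) to another, and the two would give different within-arm results.

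The outputs concerned are descriptive safety summaries that support the monotherapy safety objective. The primary and secondary efficacy analyses are unaffected. The point should be corrected, but it does not threaten the trial's main conclusions.

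**What to change.** - In the Table 24 withdrawal-column header, restate comparison 1 as high-dose drug without metformin versus overall (low- and high-dose) drug plus metformin, as re-randomised, in line with SAP 4.1.5 and 8.13. If a high-dose-only comparison is also wanted, list it separately as supplementary and not randomised.
- In the laboratory, eGFR, liver function, hepatic AE and marked-abnormality rows of that column, name the Randomised Withdrawal Subjects Data Set.
- For laboratory and eGFR change values in the withdrawal period, state change from withdrawal baseline in both Table 24 and SAP 4.7.3.1.

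The cost is SAP wording. No new data or analysis is needed, and the change concerns analysis labels only, not treatment.
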